#### LIST OF ABBREVIATIONS

ADT	Androgen deprivation therapy
AE	Adverse Event
AKT	Protein kinase B (PKB) also known as AKT
ALT	Alanine transaminase
AMPK	AMP-activated protein kinase
ASA	Aspirin
AST	Aspartate aminotransferase
ANC	Absolute neutrophil count
AR	Androgen receptor
BUN	Blood urea nitrogen
CBC	Complete blood count

Title: A Phase 2 Randomized Discontinuation Trial in Patients with Hormone-Dependent Rising Prostate-Specific Antigen Progression After Local Therapy for Prostate Cancer Evaluating the Synergy of Metformin Plus Aspirin (PRIMA Trial).

PI: [REDACTED]

CINJ	[REDACTED]
CINJOG	[REDACTED]
CI	Confidence interval
COX	Cyclooxygenase
CT	Computer Tomography
CTCAE	Common Terminology Criteria for Adverse Events
CXR	Chest x-ray
dL	Deciliter
DNA	Deoxyribonucleic acid
DSMP	Data Safety Monitoring Plan
ECOG	Eastern Cooperative Oncology Group
eCRF	Electronic case report form
EGFR	Epidermal growth factor receptor
FDA	Food and Drug Administration
GI	Gastrointestinal
IGF-I	Insulin-like growth factor I
IRS	Insulin receptor substrates
IRB	Institutional Review Board
JAK	Janus kinase
LKB1	Liver kinase B1
MAPK	Mitogen-activated protein kinases
Mg	Milligrams
mL	Milliliters
MRI	Magnetic resonance imaging
mTOR	Mammalian target of rapamycin
NCI	National Cancer Institute
NF- $\kappa$ B	Nuclear factor kappa-light chain enhancer of activated B cells
Ng	Nanograms
NIH	[REDACTED]
OR	Odds ratio
OHRS	Office of Human Research Services
OHRP	Office of Human Research Protection
PI3K	Phosphoinositide-3-kinase
PI	Principal Investigator
Pca	Prostate Cancer
PSA	Prostate specific antigen
PSA DT	Prostate specific antigen doubling time
Rb	Retinoblastoma protein
SAE	Serious adverse event
SGOT	Serum glutamic oxaloacetic transaminase
SGPT	Serum glutamic pyruvic transaminase
STAT	Signal transducer and activator of transcription
WBC	White blood cell

[figure not shown]
[REDACTED] ocol Version 8.0 12/01/2017

B

Title: A Phase 2 Randomized Discontinuation Trial in Patients with Hormone-Dependent Rising Prostate-Specific Antigen Progression After Local Therapy for Prostate Cancer Evaluating the Synergy of Metformin Plus Aspirin (PRIMA Trial).

PI: [REDACTED]

## SYNOPSIS:

### Primary endpoint:

Increase in 6 month rate of PSA and clinical progression in randomized patients from 40% in the treatment arm to 80% in the placebo arm.

**TOTAL NUMBER OF REGISTERED PATIENTS= 66 (assuming 10 patients progress prior to randomization)**

**TOTAL NUMBER OF RANDOMIZED PATIENTS= 56  
28 PATIENTS PER ARM**

**STATISTICAL ANALYSIS:** With 28 patients randomized to treatment or placebo the study will have 80% power to detect an increase in the proportion of patients with progression at 6cycles from 40% to 80% with alpha =0.05

**DEFINITION OF PSA PROGRESSION DURING RANDOMIZATION PERIOD:**  
Increase in PSA by >50%above and absolute rise of >2ng/ml

Protocol Version 8.0 12/01/2017

CINJ #. 081501

Title: A Phase 2 Randomized Discontinuation Trial in Patients with Hormone-Dependent Rising Prostate-Specific Antigen Progression After Local Therapy for Prostate Cancer Evaluating the Synergy of Metformin Plus Aspirin (PRIMA Trial).

PI: [REDACTED]

## 1. Purpose/Specific Objectives

In this phase II protocol we specifically propose the following aims:

### 1.1 Primary Endpoints

- 1.1.1 To determine the effect of metformin and aspirin on the change in PSA progression in men with rising PSA after definitive therapy for localized prostate cancer and stable disease during a run-in period with the study regimen.

### 1.2 Secondary Endpoints

- 1.2.1 To determine the feasibility and safety of administering metformin and aspirin
- 1.2.2 To determine the effect of metformin and aspirin on PSA levels and the serum obesity-related PCa biomarkers (insulin, IGF-1, IL-1 $\beta$ , IL-6, and TNF- $\alpha$ )

## 2. Background and Significance

Prostate cancer is the most commonly diagnosed cancer in males and the second leading cause of death from cancer in men. One in every six men is diagnosed with prostate cancer during their lifetime. The American Cancer Society estimates that during 2014 approximately 233,000 new cases of prostate cancer will be diagnosed and over 29,480 men will die from the disease in the U.S. Twenty to forty percent of patients undergoing radical prostatectomy [1, 2] and 30–50% of patients undergoing radiation therapy will experience biochemical recurrence within 10 years [3],[4].

While there is no current standard of care therapy in patients with PSA progression following local therapy without defined metastasis, it is of particular difficulty to make treatment decisions in this population of patients. Despite a clearer understanding of the usage of androgen deprivation therapy (ADT) in patients with metastatic disease, there is no definitive clinical trial or approach to define when and if to initiate ADT in this population with only PSA progression after local therapy [5]. Given the eventual progression to resistance to, and toxicities of, ADT, however, additional options of less toxic therapies would be impactful to this large population of patients [6, 7].

Multiple mechanisms of tumor progression and drug resistance are now understood and provide potential therapeutic targets. Most rising PSA only prostate cancer patients are hormonal sensitive and depend mainly on the classical androgen receptor-signaling pathway. This classical pathway starts with an androgen binding to the androgen receptor (AR), the complex then transports from the cytosol into the cell nucleus and binds to a specific sequence of DNA and interact with other proteins, resulting in up- or down-regulation of specific gene transcription [8]. Alternative androgen receptor-signaling pathways, such as PI3K/Akt/mTOR [9-11], MAPK [12-14], Wnt/beta-catenin [15], JAK/STAT [16], have been implicated in prostate carcinogenesis. A number of clinical trials testing inhibitors targeting the alternative androgen receptor-signaling pathways, such as Akt, EGFR inhibitors, in treating rising PSA only prostate cancer have been performed or are currently ongoing.

**Metformin activity in cancer:** Metformin is the most widely used antidiabetic drug because of its proven efficacy and limited side effects. Interestingly, recent studies have reported that metformin can block the growth of different tumor types [17, 18]. Metformin causes secondary inhibition of

Protocol Ve [REDACTED]

Title: A Phase 2 Randomized Discontinuation Trial in Patients with Hormone-Dependent Rising Prostate-Specific Antigen Progression After Local Therapy for Prostate Cancer Evaluating the Synergy of Metformin Plus Aspirin (PRIMA Trial).

PI: [REDACTED]

the mTOR complex via activating AMP-activated protein kinase (AMPK) [19]. Insulin and Insulin-like growth factor I (IGF-I) are key factors in promoting cancer development. Binding of insulin/IGF-I to their receptors results in receptor autophosphorylation and activation of receptor tyrosine kinase, followed by tyrosine phosphorylation of insulin receptor substrates, which further propagates the downstream PI3K/AKT/mTOR signaling pathway [20]. Metformin is observed to reduce hyperglycemia, improve glucose utilization, and reduce free fatty acid utilization and gluconeogenesis. Subsequently, metformin reduces insulin and IGF-1 production. Metformin may abolish mTOR activation through AMPK-independent pathway - inhibition of insulin/IGF-I signaling.

Metformin has also been shown to inhibit cyclin D1 expression and retinoblastoma protein (Rb) phosphorylation, which results in the inhibition of cell proliferation [21]. Metformin inhibits androgen-induced IGF-IR up-regulation in prostate cancer cells by disrupting membrane-initiated androgen signaling [22]. These indicate metformin might have direct inhibitory effect on prostate cancer cells.

**Aspirin activity in cancer:** Aspirin (ASA) is a salicylate drug, often used as an analgesic, an antipyretic and anti-inflammatory medication. ASA also has been widely used as an antiplatelet in the prevention of cardio-cerebrovascular diseases. ASA is non-selective and irreversibly inhibits both COX1 and COX2. ASA clearly demonstrated its role in preventing cancer death as described in a meta-analysis of eight randomized clinical trials - the largest drop in risk was for colorectal cancer and some more modest risk reductions for several other common cancers, including lung and prostate [23]. The mechanisms for its chemopreventative effects are, however, not clear yet. Various hypotheses have been proposed; the most accepted among these proposes that its anti-cancer action is mediated through COX-2 inhibition [24, 25]. Other possible mechanisms includes inhibition of NF- $\kappa$ B [26], induction of polyamine catabolism [27], inhibition of mTOR signaling [28] and activation of AMPK [29], effects on PI3K pathway [30] or its crosstalk with COX-2, and induction of apoptosis through other pathways. We recently demonstrated that COX/beta-catenin signaling pathway is activated in hematopoietic stem cell self-renewal and leukemogenesis [31]. ASA might exert its direct anti-prostate cancer effects through inhibitions of COX2, mTOR, AMPK, Wnt/beta-catenin and PI3K pathways and might be synergistic when combined with metformin.

**Metformin, aspirin and PCa tumorigenesis:** A recent non-randomized study showed that metformin use was associated with a 24% reduction in PCa mortality for every additional 6-months of post PCa diagnosis exposure (odds ratio [OR] 0.76; 95% confidence interval [CI], 0.64-0.79) compared with other antidiabetic drug use among diabetics [32]. Consistent with this finding, metformin use is also associated with a reduced risk of distant metastasis, development of castration-resistant PCa (OR=0.07, 95% CI 0.008-0.55) following biochemical recurrence, and overall mortality among men receiving external beam radiation [33]. A randomized trial demonstrated that metformin use (500mg three times a day for 41 days) before surgery reduced cancer proliferation rate by 32% in the surgical specimen compared with pre-surgical biopsy specimen [34]. In addition, a recent phase 2 trial in patients with castration-resistant PCa showed metformin treatment for 24 weeks may induce disease stabilization and prolong the prostate-

Protocol Version 8.0 12/01/2017

Title: A Phase 2 Randomized Discontinuation Trial in Patients with Hormone-Dependent Rising Prostate-Specific Antigen Progression After Local Therapy for Prostate Cancer Evaluating the Synergy of Metformin Plus Aspirin (PRIMA Trial).

PI: [REDACTED]

specific antigen (PSA) doubling time [35]. Furthermore, metformin significantly inhibited the tumor growth in LNCaP xenograft mice [36] and reduced PIN development and PCa lesions in Hi-Myc mice [37]. For aspirin, there is some evidence for a protective effect against PCa [38-40], however, controversy data suggesting no association has been reported [41]. In a longitudinal cohort study of 5955 patients with localized PCa who were followed for up to 10 years, Choe *et al.* recently reported that aspirin use was independently associated with a lower risk of PCa-specific mortality (adjusted hazard ratio, 0.43; 95% CI 0.21-0.87) [42]. A systematic meta-analysis showed that aspirin use decreased the total risk of PCa by 17% (95% CI 0.77-0.89) and decreased the risk of advanced PCa by 19% (95%CI 0.72-0.92) [43, 44]. **These results suggest that metformin and aspirin could be used in preventive and/or therapeutic strategies for PCa.**

**Metformin, aspirin and the NF-κ B/STAT3 signaling pathway:** NFκB, a mediator of inflammatory response, plays a significant role in carcinogenesis and is now emerging as a link between inflammation and cancer. Abundant data supports a key role for the NFκB signaling pathway in controlling the initiation and progression of human cancer. The NFκB pathway is an important contributor to PCa metastasis [45-47] and activation of NFκB signaling promotes castrate-resistant growth of PCa [48, 49]. STAT3 mediates a complex spectrum of cellular responses including inflammation, cell proliferation and apoptosis. Constitutively activated STAT3 has been implicated in a number of cancers, including PCa [50-52]. More important, inhibition of STAT3 has been shown to induce apoptosis in PCa cells [51-53], suggesting STAT3 may be an excellent molecular target for PCa prevention and treatment. Aspirin has been extensively studied as a COX inhibitor (Figure 1). It has also been shown to inhibit NFκB activation [54, 55], and to induce apoptosis through down-regulation of interleukin (IL)-6-STAT3 signaling pathways [56, 57]. These data indicate that NFκB/STAT3 play a critical role in the prevention of aspirin against PCa. Metformin has also been shown to inhibit STAT3 phosphorylation and downstream signaling in triple-negative breast cancer cells [58], and increase the sensitivity of resistant cells to cisplatin by suppressing STAT3 activity without activation of AMPK $\alpha$ , suggesting STAT3 is a critical regulator of metformin action [59].

**Metformin, aspirin and AMPK/mTOR signaling pathway:** Metformin may diminish the effects of insulin on tumor development and growth through inhibition of hepatic gluconeogenesis or increase insulin sensitivity, thus leading to reduced circulating insulin and IGF-1 levels (Figure 1) [60, 61]. Binding of insulin/IGF-1 to their receptors results in receptor autophosphorylation and activation of receptor tyrosine kinase, followed by tyrosine phosphorylation of insulin receptor substrates (IRS 1-4), which further propagates the downstream phosphatidylinositol-3-kinase (PI3K)/AKT/mTOR signaling pathway [20]. Metformin may abolish mTOR activation through inhibition of insulin/IGF-1 signaling an AMPK-independent mechanism, or through liver kinase B1 (LKB1)-mediated activation of AMPK an AMPK-dependent mechanism [62]. While AMPK-dependent suppression of mTOR signaling remains the key candidate mechanism of antitumor action of metformin, of particular note is that metformin may also target the inflammatory component, leading to tumor reduction [63, 64]. Salicylate, as a main metabolite of aspirin, was recently reported to directly activate AMPK activity [65]. Din *et al.* recently showed that aspirin alone or combination of aspirin and metformin activates AMPK and inhibits mTOR signaling in

[figure not shown]
Proto: [REDACTED]

Title: A Phase 2 Randomized Discontinuation Trial in Patients with Hormone-Dependent Rising Prostate-Specific Antigen Progression After Local Therapy for Prostate Cancer Evaluating the Synergy of Metformin Plus Aspirin (PRIMA Trial).

[figure not shown]
PI: [REDACTED]

colorectal cancer cells [66]. Potential mechanisms of synergistic action of these two agents in pancreatic cancer have been reviewed comprehensively [67].

**In vitro mechanism studies:** Recent work in the laboratory of [name] and Rutgers CINJ demonstrates that the combination of metformin and aspirin at low concentrations had significant synergistic effects on the inhibition of cell viability and colony formation (Figure 3), and resulted in a significant decrease in the phosphorylation of mTOR and STAT3 (Figure 4) in two PCa cell lines LnCap and Du145.

**Fig. 1. Metformin and aspirin synergistically inhibit cell viability and colony formation in both LnCap and Du145 cells.** A and B, MTT assay for the cell viability of LnCap and Du145, respectively. Cells were treated with indicated concentrations of metformin and aspirin, alone or in combination for 72 h; C, Clonogenic assay for LnCap and Du145. Cells were treated with metformin (5 mM) and aspirin (2 mM), alone or in combination for 72 h; then 1000 treated or untreated cells per well were seeded in 6-well plates and cultured for another 10 days; D, Quantification of colony formation assay in LnCap and Du145 cells, respectively. Met, Metformin; Asp, Aspirin: \*P < 0.05, compared to the control, \*\*P < 0.05 for the test of synergy.

**Fig.2. Metformin and aspirin synergistically inhibit the phosphorylation of mTOR and STAT3 in both LnCap (A) and Du145 (B) cells.** Cells were treated with 5 mM metformin, 2 mM aspirin or a combination for 24, 48, or 72 h, respectively. Protein expression levels of mTOR, p-mTOR, STAT3 and p-STAT3 were determined by Western blot. The ratios of p-mTOR/mTOR and pSTAT3/STAT3 were calculated and normalized to the control. Cont, Control; Met, Metformin; Asp, Aspirin; Comb, Combination.

Title: A Phase 2 Randomized Discontinuation Trial in Patients with Hormone-Dependent Rising Prostate-Specific Antigen Progression After Local Therapy for Prostate Cancer Evaluating the Synergy of Metformin Plus Aspirin (PRIMA Trial).

PI: [REDACTED]

**Clinical trial:**

Based on compelling epidemiological and preclinical data suggesting that metformin and aspirin may act synergistically to inhibit prostate cell growth, we will conduct a placebo-controlled Phase II intervention study, using a randomized discontinuation design. The primary objective is to determine if metformin plus aspirin prolongs the PSA doubling time compared to use of metformin alone in patients who have stable PSA values during a 4 month run in period of treatment with both agents.

In this study a randomized discontinuation design will be used in order to address some of the unique considerations in testing a regimen that would be considered effective if it leads to disease stabilization and that depends on modulation of a blood based biomarker as the primary determinant of efficacy.

As noted by Ratian et.al, “a randomized discontinuation design initially treats all patients with the study agent (stage 1) and then randomizes in a double-blind fashion to continuing therapy or placebo only those patients whose disease is stable (stage 2). This design allows the investigators to determine if apparent slow tumor growth is attributable to the drug or to selection of patients with naturally slow-growing tumors. By selecting a more homogeneous population, the randomized portion of the study requires fewer patients than would a study randomizing all patients at entry. The design also avoids potential confounding because of heterogeneous tumor growth. Because the two randomly assigned treatment groups each comprise patients with apparently slow growing tumors, any difference between the groups in disease progression after randomization is more likely a result of the study drug and less likely a result of imbalance with respect to tumor growth rates”. Utilization of this design allowed investigators to determine that sorafenib caused statistically meaningful disease stabilization that was subsequently confirmed in a phase III trial leading to drug approval.

In patients with rising PSA, drugs causing disease stabilization would be expected to lead to a slowing in the rate of rise in the PSA, which can also be expressed as a lengthening of the PSA doubling time. Multiple prior phase II trials for men with rising PSA, including several randomized placebo controlled trials, have assessed changes in PSA doubling time as an endpoint. In these trials it was noted that patients in the placebo arm often have an increase in the PSADT after going on study. As noted by Paller et al., in a Rosiglitazone trial involving 106 patients, 73% of patients on placebo had an increase of PSADT in excess of 100%, and 31% exceeded 200% in PSADT lengthening. In an Atrasentan trial involving 222 patients, 78% of the patients on placebo had a lengthening of PSADT. In a celecoxib trial involving 78 patients, 20% of the patients on placebo had >200% increase of PSADT. In these studies, the increase in pre and on-treatment PSA doubling time has been attributed to difference between spacing interval and number of PSA values collected in an uncontrolled “pre-study period compared to the regular intervals at which PSA values are collected once on study”.

In the current design all subjects will receive study therapy for 4 cycles. During this period PSA will be measured at monthly intervals in order to determine a PSA doubling time in a uniform manner, and to obtain a relatively homogeneous population of patients for randomization. Patients

Protocol Version 8.0 12/01/2017

Title: A Phase 2 Randomized Discontinuation Trial in Patients with Hormone-Dependent Rising Prostate-Specific Antigen Progression After Local Therapy for Prostate Cancer Evaluating the Synergy of Metformin Plus Aspirin (PRIMA Trial).

PI: [REDACTED]

meeting the study specified definition of stable disease will then proceed to randomization while patients meeting criteria for PSA progression will come off study and those patients with PSA response will continue on therapy until the study definition of disease progression is met.

After the run in phase patients meeting the criteria for stable disease will be randomized to continue therapy with metformin and aspirin or to placebo metformin, and placebo aspirin.

The secondary objective of this study is to determine whether the intervention may modify the PSA levels and the serum obesity-related PCa biomarkers. The tolerability of and compliance of metformin and aspirin treatment in these subjects will also be evaluated.

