#### **4.1 Disease Assessment After Run In Stage:**

After 4 cycles of treatment patients with disease progression (PSA increase of >50% and minimum of 2ng/ml rise in PSA) will come off study. Patients with disease response (>25% decline in PSA) will continue on study agents.

Patients with stable disease (not meeting criteria for progression or stable disease) will be randomized to continue on the study regimen or receive placebo therapy for 6 cycles.

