#### **4.3 Randomization Stage Treatment:**

Patients meeting criteria for randomization will be randomized to continue therapy with metformin 500 mg in the morning and 1000 mg at night and aspirin 81 mg per day and or to placebo metformin and, placebo aspirin.

Randomization will be performed based on a randomization schedule generated by statistician ([name]) using a stratified randomization method in order that the numbers of obese patients (BMI  $\geq$  30) on each group are balanced.

Protocol Version 8.0 12/01/2017

Title: A Phase 2 Randomized Discontinuation Trial in Patients with Hormone-Dependent Rising Prostate-Specific Antigen Progression After Local Therapy for Prostate Cancer Evaluating the Synergy of Metformin Plus Aspirin (PRIMA Trial).

PI: [REDACTED]

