## **16.2 Outcome Measures**

Difference in the stable PSA rates after 6 cycles of metformin and aspirin or placebo therapy will be calculated in patients who have received 4 cycles of open label treatment during the “run in phase”

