## **16.3 Sample Size and Statistical Analysis**

In this study, we hypothesize that patients with stable PSA after 4 cycles of open label treatment who are then treated with 6 cycles of metformin and aspirin will have a 40% rate of PSA or clinical progression compared to 80% rate of progression in patients treated with placebo. With 28 patients randomized to treatment or placebo the study will have 80% power to detect an increase in the proportion of patients with progression at 6 cycles from 40% to 80% with alpha =0.05. Assuming that approximately 10 patients progress prior to randomization, a total of 66 patients will be entered on this study.

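### Adjusting the primary comparison for run-in PSA growth and PSA level would gain precision at almost no cost; the stated 80% power is not in error

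*Combined protocol and SAP*

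**What the plan says.** Section 2 (Clinical trial) takes its rationale from a cited design paper: both randomised groups consist of men with apparently slow-growing disease, so a difference is "less likely a result of imbalance with respect to tumor growth rates". It adds that monthly run-in PSA readings serve to give a doubling time measured in a uniform way and "to obtain a relatively homogeneous population of patients for randomization".

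The rules that implement this are:

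- **4.1.** Men whose PSA rises by more than 50% and by at least 2 ng/mL leave the study. "Patients with disease response (>25% decline in PSA) will continue on study agents". The rest are randomised. (The wording that defines stable disease refers to itself; I read it as neither progression nor response.)
- **4.3.** Allocation uses a "stratified randomization method in order that the numbers of obese patients" (BMI of 30 or more) are balanced. No other factor is named.
- **4.5.** Progression after randomisation is PSA more than 50% above baseline with a 2 ng/mL increase, or radiographic progression. Which reading is the baseline is not stated.
- **16.2.** "Difference in the stable PSA rates after 6 cycles of metformin and aspirin or placebo therapy will be calculated". Neither 16.2 nor 16.3 names a test or a covariate.
- **16.3.** Men on treatment "will have a 40% rate of PSA or clinical progression compared to 80% rate of progression in patients treated with placebo". For this contrast the plan claims 80% power from 28 men per arm, at alpha 0.05.

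The run-in doubling time described in Section 2 is used in neither the allocation nor the primary comparison.

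**The concern.** The endpoint is PSA growth, and in the continuing arm treatment does not change at randomisation. A man's growth during the run-in should therefore say a good deal about whether he crosses the threshold in the next 6 cycles. Because of the 2 ng/mL condition, so should his PSA level. If the stable category is wide, the randomised men still differ on both measures, and with 28 per arm those differences will often be unequal between arms by chance.

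At stake is precision. The trial already collects the readings that could remove part of this noise. Choosing an adjustment only after an imbalance has been seen would be less credible than prespecifying it.

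**Working it through.** **1. The plan's own figure.** Inputs from 16.3: 40% versus 80%, alpha 0.05 (two-sided assumed), 80% power.

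- Uncorrected: n = [1.96·√(2·0.6·0.4) + 0.842·√(0.4·0.6 + 0.8·0.2)]² / 0.4² = (1.358 + 0.532)² / 0.16 = 22.3, so 23 per arm.
- With continuity correction: (22.3/4)·[1 + √(1 + 4/(22.3·0.4))]² = 27.1, so 28 per arm.

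The plan's 28 is reproduced. Fisher's exact test at 28 per arm has 82.3% power.

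**2. Width of the stable window (4.1), over 16 weeks.** The log slope runs from ln(0.75)/16 = −0.018 to ln(1.5)/16 = +0.025 per week. That is a halving time of 9.6 cycles to a doubling time of 6.8 cycles. A man counts as progressing only if his PSA ratio exceeds both 1.5 and 1 + 2/PSA. The second term governs below 4 ng/mL: ×2 at 2 ng/mL, ×3 at 1, ×11 at 0.2 (the lowest eligible value after surgery, 5.1.3a).

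A man at the 4-month doubling-time limit of 5.1.3d rises 2^(16/17.4) = ×1.89 in the run-in. Below 2/0.89 ≈ 2.2 ng/mL he cannot meet the progression rule if growth is unchanged. With the 6-cycle limit in Section 4, the figures are 2^(4/6) = ×1.59 and 2/0.587 ≈ 3.4 ng/mL. In low-PSA men, then, the run-in removes few or no fast growers.

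**3. Why growth and level are plausibly prognostic.** If growth continues unchanged, the +50% part is met within 24 weeks when the run-in ratio exceeded 1.5^(16/24) = 1.31 (randomisation PSA as baseline) or 1.5^(16/40) = 1.18 (C1D1 PSA as baseline). Both cut-offs lie inside the window. A man at its upper edge (PSA 4 or more) rises 1.5^(24/16) = ×1.84; a flat man does not progress.

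**4. Size.** Split the 56 men at the median of run-in growth. Let D be the gap in progression risk between the faster and slower halves; the documents give no value, so D is assumed. The number of faster growers in one arm is hypergeometric, with SD √(28·0.25·28/55) = 1.89. The between-arm difference in their share then has SD 2·1.89/28 = 13.5 points, and the chance shift in the primary difference is that imbalance times D. Power comes from 200,000 simulated trials per row, comparing the unadjusted two-proportion test with a Mantel-Haenszel test stratified by growth half.

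| D | 95% limit of shift, normal / discrete (points) | Power unadjusted → adjusted, continuity-corrected | Same, uncorrected |
|---|---|---|---|
| 0 | 0 / 0 | 80.8% → 80.8% | 88.2% → 87.6% |
| 0.2 | 5.3 / 5.7 | 80.7% → 82.8% | 88.1% → 89.3% |
| 0.3 | 7.9 / 8.6 | 80.7% → 85.7% | 88.2% → 91.7% |
| 0.4 | 10.6 / 11.4 | 80.4% → 89.5% | 88.0% → 94.6% |

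With a median split, an 80% placebo rate allows D no larger than 0.4 in that arm (100% versus 60%). Under a null with a 60% rate in both arms, D could reach 0.8, with a 95% limit of 21 to 23 points.

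**5. Validity.** Under the null, across all D examined, the unadjusted test rejects in 4.5–4.8% of trials uncorrected, and in about 2% with continuity correction.

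**6. Slope versus level.** A patient-level simulation assumed exponential growth, PSA CV 10–15%, between-man slope SD 0.008–0.016 per week and median PSA 8 ng/mL. It used permutation tests adjusted for PSA level alone or for slope. With the randomisation baseline, power was 89% vs 93%, 89% vs 92% and 87% vs 86%. With the C1D1 baseline, slope gave 92–98% and level 88–90%.

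A separate simulation, also on assumed inputs, applied one test with and without covariates. Unadjusted power was about 88%. Adjusting for slope gave 88–96% (randomisation baseline) or 91–99% (C1D1 baseline). Adding PSA level gave 88–98% or 94–99%. Slope added almost nothing when growth varied little, PSA noise was high and the baseline was the randomisation PSA.

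**The case against.** The strongest reply is that nothing here is invalid. Randomisation makes chance imbalance part of the standard error, which is √[(0.24 + 0.16)/28] = 12 points at 40% versus 80%. The planned rates are marginal, so variation in growth is already inside them. Section 2 speaks only of what is less likely and of relative homogeneity, and the run-in does remove some men. All of this stands, and it rules out four stronger readings:

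- **That the trial falls short of 80% power.** Step 1 shows it does not.
- **That the comparison is confounded or its error rate inflated.** False-positive rates above 5% arise only when one conditions on an imbalanced allocation; the overall rate is kept.
- **That the shift has a fixed ceiling.** Any single figure reflects one assumed gap. A 12-point 95% limit, for instance, needs D = 0.12/(1.96·0.135) ≈ 0.45.
- **That Section 2 promises balance and is contradicted.** Its wording is comparative.

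Two further objections limit the size of the point. If the drug effect varies between men (assumed SD 0.02 per week), on-drug growth says less about growth on placebo: simulated placebo progression by run-in slope tertile flattens to 76/80/84%. And if PSA is low (assumed median 2 ng/mL, randomisation baseline), active-arm progression is 31/43/45% by slope tertile but 8/43/69% by PSA-level tertile. Slope alone would therefore be the wrong covariate set. Both objections are accepted, and they are why PSA level belongs in the adjustment.

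**Conclusion.** This is a cheap improvement, not an error in the stated power. The stable window leaves wide variation in growth, allocation balances obesity only, and the run-in PSA series goes unused in the primary comparison. The unadjusted analysis is valid and meets its stated power, but it forgoes precision.

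For an assumed risk gap of 0.2 to 0.4 between run-in growth halves, adjustment adds about 2 to 9 points of power on the continuity-corrected test (about 1 to 7 uncorrected). The 95% limit of the chance shift is about 5 to 11 points. The upper end assumes the largest gap that an 80% placebo rate permits in both arms; the lower end shades to no gain if growth is weakly prognostic. The size also depends on which PSA is the baseline in 4.5, which the protocol leaves open.

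**What to change.** In 16.3, prespecify the following:

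- The primary comparison of progression at 6 cycles is adjusted for the least-squares slope of log PSA over the C1D1-to-randomisation readings, log PSA at randomisation, and the BMI stratum.
- The test is one that holds the 5% level at this sample size, for example a stratified or re-randomisation test.
- The covariate-standardised difference in rates is reported, with the unadjusted difference as a supporting result.

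State which PSA reading is the baseline in 4.5, and reconcile the two entry doubling-time limits (Section 4 and 5.1.3d), since both affect how much growth varies among randomised men.

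A run-in PSA stratum in 4.3 is optional. At D = 0.4 it raises adjusted power only from 89.5% to 90.2%, and it makes four cells for 56 men. If it is added, the test must use it: with the stratum in the allocation but not in the analysis, uncorrected type I error falls to 3.0% at D = 0.4 and a 60% rate.

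The cost is a few sentences, with no extra visits, assays or patients. The downside is two or three model terms on 28·0.4 + 28·0.8 ≈ 34 expected events and about 22 non-events, which is why a small-sample method is needed.
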